9.4.2.1.3. Major Secondary Endpoint Analyses

The major secondary endpoints are:

- Clinical remission at Week I-12.
- Symptomatic remission at Week I-12.
- Endoscopic healing at Week I-12.
- Histologic-endoscopic mucosal healing at Week I-12.
- Endoscopic normalization at Week I-12.

The same treatment failure rules that were specified for the primary endpoint analysis will also be used for the major secondary endpoints (Section 9.4.2.1.2). Participants who are missing any or all of the 3 Mayo subscores that compose the modified Mayo score or who do not return for evaluation at Week I-12 will be considered not to have achieved clinical remission. Participants who are missing both stool frequency and rectal bleeding subscores at Week I-12 will be considered not to have achieved symptomatic remission at Week I-12. Participants who have missing endoscopy subscore at Week I-12 will be considered not to have achieved endoscopic healing, endoscopic normalization, or histologic-endoscopic mucosal healing at Week I-12.

For testing of the major secondary endpoints, the efficacy of each guselkumab group versus placebo will be compared. For all statistical comparisons of the major secondary endpoints, a CMH test (2-sided) stratified by ADT-Failure status (Yes/No) and concomitant use of corticosteroids at baseline (Yes/No) will be used.

The study is not being powered to detect treatment differences between guselkumab and placebo for these major secondary endpoints. These endpoints will not be multiplicity-controlled for analysis purposes, and all p-values will be considered nominal.

9.4.2.1.4. Other Endpoint Analyses

Comparisons between each of the guselkumab groups and the placebo group at Week I-12 will be made for each of the endpoints.

Analyses suitable for categorical data (eg, chi-square test or CMH test, as appropriate) will be used to compare the proportion of participants achieving selected endpoints (eg, clinical response). In case of rare events, the Fisher's exact test will be used for treatment comparisons.

Continuous response parameters will be compared using an ANOVA or covariance (ANCOVA), unless otherwise specified. If the normality assumption is in question, an ANOVA or ANCOVA on the van der Waerden normal scores will be used.

All statistical testing will be performed at the 2-sided 0.05 significance level. No adjustments for multiple comparisons will be made for these other efficacy endpoints and nominal p-values will be presented.

9.4.2.2. Induction Study 2 (Phase 3 Induction Study)

9.4.2.2.1. Population for Efficacy Analysis

Unless otherwise noted, efficacy analyses will be based on the **Full Analysis Set**, which is defined as all randomized participants with a modified Mayo score of 5 to 9 who receive at least 1 dose of study intervention. Participants will be analyzed according to the intervention group to which they were randomized regardless of the intervention they actually received.

9.4.2.2.2. Primary Endpoint Analysis

The primary endpoint is clinical remission at Week I-12, defined as a stool frequency subscore of 0 or 1, a rectal bleeding subscore of 0, and an endoscopy subscore of 0 or 1 with no friability present on the endoscopy, where the stool frequency subscore has not increased from induction baseline. The analyses will be based on the Full Analysis Set.

Participants who have a colectomy or ostomy, have protocol-prohibited medication changes (to be defined in the SAP), or who discontinued study intervention due to reasons other than COVID-19 related reasons or a regional crisis, including unsatisfactory therapeutic effect or an AE of worsening UC, before the Week I-12 visit will be considered as treatment failures and considered not to be in clinical remission, regardless of the actual modified Mayo score. For participants who discontinued study intervention due to COVID-19 related reasons (excluding COVID-19 infection) or regional crisis, their observed clinical remission status at Week I-12 will be used if available. After accounting for the treatment failure rules, participants who are missing any or all of the 3 Mayo subscores that compose the modified Mayo score or who do not return for evaluation at Week I-12 will be considered not to be in clinical remission.

A precise description of the treatment effect to be estimated from the study will be described in the estimand framework. The primary estimand will use a hybrid strategy for the intercurrent events. Details on the primary estimand and other estimand definitions will be described in the SAP.

For testing of the primary endpoint, the efficacy of the guselkumab group versus placebo will be compared. A CMH test (2-sided) stratified by ADT-Failure status (Yes/No) and concomitant use of corticosteroids at baseline (Yes/No) will be used. The comparison between guselkumab and placebo will be controlled at the 2-sided 0.05 significance level. The study will be considered positive if the guselkumab group is significantly different from the placebo group for the primary endpoint.

To examine the robustness of the primary endpoint analysis, sensitivity analyses of the primary endpoint will be conducted using different missing data approaches; these analyses will be described in the SAP.

Subgroup analyses of the primary endpoint will be performed based on demographic and baseline disease characteristics, baseline use and history of use of UC medications (including ADT-Failure status), and molecular predictive signature status at baseline.

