6.3. Measures to Minimize Bias: Randomization and Blinding

Randomization will be used to minimize bias in the assignment of participants to treatment groups, to increase the likelihood that known and unknown participant attributes (eg, demographic and baseline characteristics) are evenly balanced across treatment groups, and to enhance the validity of statistical comparisons across treatment groups. Blinded treatment will be used to reduce potential bias during data collection and evaluation of clinical endpoints.

Intervention Allocation

Central randomization will be implemented in all 3 studies based on a computer-generated randomization schedule prepared before the studies by or under the supervision of the sponsor. In Induction Study 1, participants will be randomly assigned to 1 of 3 treatment groups in a 1:1:1 ratio. In Induction Study 2, participants will be randomly assigned to guselkumab or placebo in a 3:2 ratio, respectively. In both Induction Study 1 and Induction Study 2, the randomization will be balanced by using randomly permuted blocks and will be stratified by ADT-Failure status (ie, participants who had an inadequate response or failure to tolerate TNF α antagonists, vedolizumab, or tofacitinib) (Yes/No), region (Eastern Europe, Asia, or rest of world), and concomitant use of corticosteroids at baseline (Yes/No). In the Maintenance Study, participants will be randomly assigned to 1 of 3 treatment groups in a 1:1:1 ratio. The randomization will be balanced by using randomly permuted blocks and will be stratified by clinical remission status at maintenance baseline (Yes/No), concomitant use of corticosteroids at maintenance baseline (Yes/No), and induction dose treatment (guselkumab 400 mg, guselkumab 200 mg, placebo crossover [guselkumab 200 mg], and placebo crossover [guselkumab 400 mg, if chosen as the Phase 3 guselkumab induction dose]). For all 3 studies, the Interactive Web Response System (IWRS) will assign a unique treatment code, which will dictate the treatment assignment and matching study intervention kit(s) for the participant. The requestor must use his or her own user identification and personal identification number when contacting the IWRS and will then be given the relevant participant details to uniquely identify the participant.

Blinding

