9.2.2. Induction Study 2 (Phase 3 Induction Study)

Sample sizes were determined by the power to detect a significant difference in clinical remission at Week I-12 (primary endpoint) between the guselkumab group and the placebo group using a 2-sided chi-square test with a 0.05 significance level. The study is sized such that the guselkumab therapy achieves $\geq 90\%$ power for the primary endpoint compared with placebo.

The assumptions for the sample size calculations were also based on data from CNTO1275UCO3001. Data from mirikizumab were also taken into consideration ([Sandborn 2018](#)).

Clinical remission at Week I-12

In CNTO1275UCO3001, the proportions of participants in clinical remission at Week 8 based on a stool frequency subscore of 0 or 1, a rectal bleeding subscore of 0, and an endoscopy subscore of 0 or 1 with no friability present on endoscopy, where the stool frequency subscore did not increase from induction baseline, were 6.9% and 19.3% for placebo and ustekinumab 6 mg/kg, respectively, for a treatment difference of 12.4%, with about 320 participants in each group. The clinical remission rate (4.8% at Week 12) for placebo from the Phase 2 study of another IL-23 mAb (ie, mirikizumab) in similar population was also considered ([Sandborn 2018](#)). The clinical remission rates for different dose levels of mirikizumab did not demonstrate a clear dose-response trend and varied between 11.5% and 22.6%, with about 60 participants in each treatment group ([Reich 2019](#)).

Based on the data above, the clinical remission rates at Week I-12 are assumed to be 8-10% for placebo and 20-24% for the selected guselkumab dose.

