Assuming 8% clinical remission in the placebo group and 20% in the guselkumab group, 175 participants per group (350 participants in total) will provide statistical power of 90% for comparison of guselkumab versus placebo at a significance level of 0.05 (2-sided). However, to provide a sufficient number of participants for the primary analysis population in the Maintenance Study, the sample size for Induction Study 2 was increased to at least 560 participants in the primary analysis population and the randomization allocation was slightly skewed to guselkumab (3:2) to generate a sufficient number of guselkumab clinical responders. [Table 6](#) shows the power for detecting a treatment difference between the guselkumab group and the placebo group based on different proportions of participants in clinical remission at Week I-12 with a fixed sample size of 560 participants.

Table 6: Power to Detect a Treatment Effect for Guselkumab Based on the Proportion of Participants Achieving Clinical Remission at Week I-12 for Induction Study 2			
Primary Endpoint of Clinical Remission at Week I-12			
Placebo (n = 224)	Guselkumab IV (n = 336)		Power
8%	18%		93%
8%	20%		98%
8%	22%		>99%
10%	20%		90%
10%	22%		97%
10%	24%		99%

A sample size of 560 participants in the primary analysis population also provides sufficient power for the majority of the major secondary endpoints. The given sample size will provide approximately 90% power for the following major secondary endpoints: symptomatic remission at Week I-12 (40% vs 25% for guselkumab vs placebo); endoscopic healing at Week I-12 (27% vs 14% for guselkumab vs placebo); clinical response at Week I-12 (60% vs 30% for guselkumab vs placebo); symptomatic remission at Week I-4 (33% vs 20% for guselkumab vs placebo); IBDQ remission at Week I-12 (47% vs 32% for guselkumab vs placebo); histologic-endoscopic mucosal healing at Week I-12 (17% vs 8% for guselkumab vs placebo); and fatigue response at Week I-12 (44% vs 25% for guselkumab vs placebo). The assumptions noted above are based on the CNTO1275UCO3001 data.

The total sample size across Induction Study 1 and Induction Study 2, for randomized participants with a modified Mayo score of 5 to 9, is a target of approximately 950 participants. However, the program also enrolled participants with a modified Mayo score of 4; therefore, the total sample size for the program is estimated to be 1000 participants.

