(CMH) test (2-sided) stratified by ADT-Failure status (Yes/No) and concomitant use of corticosteroids at baseline (Yes/No) will be used. A step-up multiple testing procedure (Hochberg 1988) will be used to control the Type-I error at a 2-sided 0.05 significance level over the comparisons for the primary endpoint. For this procedure, if p-values for both guselkumab treatment groups are ≤ 0.05 , then it will be concluded that both guselkumab treatment groups are effective compared with placebo. Otherwise, the smaller of the 2 p-values will be compared with $\alpha = 0.025$; if that p-value is ≤ 0.025 , then it will be concluded that the guselkumab treatment group associated with the smaller p-value is effective compared with placebo. The study will be considered positive if at least 1 guselkumab group is significantly different from the placebo group for the primary endpoint.

To examine the robustness of the primary endpoint analysis, sensitivity analyses of the primary endpoint will be conducted using different missing data approaches; these analyses will be described in the SAP.

Subgroup analyses of the primary endpoint will be performed based on demographic and baseline disease characteristics, baseline use and history of use of UC medications (including ADT-Failure status), and molecular predictive signature status at baseline.

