9.4.2.2.3. Major Secondary Endpoint Analyses

The major secondary endpoints are:

- Symptomatic remission at Week I-12.
- Endoscopic healing at Week I-12.
- Clinical response at Week I-12.
- Symptomatic remission at Week I-4.
- IBDQ remission at Week I-12.
- Histologic-endoscopic mucosal healing at Week I-12.
- Fatigue response at Week I-12.
- Symptomatic remission at Week I-2.
- Endoscopic normalization at Week I-12.

Similar treatment failure and missing data rules that were specified for these endpoints in Section 9.4.2.2.2 will be used for these major secondary endpoints, with the exception that for the major secondary endpoints of symptomatic remission at Week I-4 and Week I-2 the treatment failure events will be limited to only those that occurred prior to the Week I-4 or Week I-2 visit, respectively (Section 9.4.2.1.3).

For testing of the major secondary endpoints, the efficacy of the guselkumab group versus placebo will be compared. For all statistical comparisons of the major secondary endpoints, a CMH test

(2-sided) stratified by ADT-Failure status (Yes/No) and concomitant use of corticosteroids at baseline (Yes/No) will be used.

A fixed sequence testing procedure will be used to control for multiplicity over the primary and major secondary endpoints. That is, the major secondary endpoints will be tested at the 2-sided 0.05 significance level after the test on the primary endpoint. However, if an endpoint is not significant, all subsequent tests in the hierarchy will be considered not to be significant, and the p-values associated with those tests will be considered to be nominal. The testing order of these major secondary endpoints will be specified in the SAP. Note that the ranking order for the major secondary endpoints is different for the US-specific and global testing procedures due to regional preferences. The major secondary endpoint of IBDQ remission at Week I-12 will not be included in the US-specific testing procedure.

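### Induction Study 2 randomises within region strata, but its primary and major secondary CMH tests omit region without explanation: a minor mismatch that leaves the test valid and at most slightly conservative

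*Protocol*

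**What the plan says.** Protocol 6.3 describes the allocation: "In both Induction Study 1 and Induction Study 2, the randomization will be balanced by using randomly permuted blocks". The strata are ADT-failure status together with "region (Eastern Europe, Asia, or rest of world), and concomitant use of corticosteroids at baseline (Yes/No". Protocol 4.1.2 gives the same three factors for Induction Study 2.

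The analysis sections use two of the three. For the primary endpoint, clinical remission at Week I-12, Protocol 9.4.2.2.2 says: "A CMH test (2-sided) stratified by ADT-Failure status (Yes/No) and concomitant use of corticosteroids at baseline (Yes/No) will be used". For the major secondary endpoints, Protocol 9.4.2.2.3 again specifies a CMH test "2-sided) stratified by ADT-Failure status (Yes/No) and concomitant use of corticosteroids at baseline (Yes/No) will be used". Neither section explains why region is left out. Section 9 refers the reader to the SAP for specific details. The SAP supplied covers only the Maintenance Study, and its Introduction says that the induction studies have separate SAPs.

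**The concern.** When allocation is blocked within a factor, between-region variation is removed from the treatment comparison by design. An analysis that ignores the factor still counts that variation as error. If region is prognostic, the test is then somewhat conservative and some power is lost.

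The documents give one reason why region might matter. Protocol 9.4.2.2.2 has a separate rule for participants who stop treatment because of a regional crisis: observed status is used if available, and otherwise they count as not in remission. The Maintenance SAP places that crisis in Russia and Ukraine (5.3.2) and lists both countries under Eastern Europe (5.10.6), which is one of the three randomisation regions.

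The possible stake is the testing sequence. Protocol 9.4.2.2.3 tests the major secondary endpoints in a fixed order, so one miss makes all later p-values nominal. Protocol 9.2.2 states only about 90% power for seven of these endpoints.

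**Working it through.** **1. Strata.** Randomisation: 2 (ADT-failure) x 3 (region) x 2 (corticosteroids) = 12. Analysis: 2 x 2 = 4. With 560 participants, 12 strata average 560/12 = 46.7 each.

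**2. The plan's own figures.** Protocol 9.2.2 sizes the study with a "2-sided chi-square test with a 0.05 significance level". The usual formula is n per group = [1.960 x sqrt(2 x pbar x (1 - pbar)) + 1.282 x sqrt(p0(1 - p0) + p1(1 - p1))]^2 / (p1 - p0)^2. With p0 = 0.08, p1 = 0.20 and pbar = 0.14, this is (0.962 + 0.619)^2 / 0.0144 = 173.6, so 174. The plan states 175, at which power is 90.2%.

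Table 6 has 224 placebo and 336 guselkumab participants. For 10% versus 20%, pbar = (22.4 + 67.2)/560 = 0.16. The null standard error is sqrt(0.16 x 0.84 x (1/224 + 1/336)) = 0.0316, and the standard error under the alternative is sqrt(0.09/224 + 0.16/336) = 0.0296. Power is Phi[(0.10 - 1.960 x 0.0316)/0.0296] = Phi(1.283) = 90.0%. The six rows of Table 6 come out at 93.2, 98.2, 99.6, 90.0, 96.9 and 99.2%, against the stated 93, 98, >99, 90, 97 and 99%. These are unstratified calculations, so none depends on region.

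**3. Effect of adding region.** Simulation, 100,000 trials per scenario: N = 560, 3:2 permuted blocks within the 12 strata. The CMH statistic is [sum(a - n1 x m/T)]^2 / sum[n1 x n0 x m x (T - m) / (T^2 x (T - 1))]. Within each stratum, a is guselkumab remissions, m total remissions, n1 and n0 the arm sizes and T the total. The statistic is compared with 3.84.

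Assumptions, because the documents give no such figures: block size 5; 45% ADT-failure (inside the planned 40 to 50% range); 40% on corticosteroids; region shares 40/20/40%; odds ratios for remission of 0.5 for ADT-failure and 0.8 for corticosteroids. The regional odds ratios were varied.

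Rejection rates in %, 4 strata -> 12 strata:

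| Regional odds ratios (Eastern Europe / Asia / rest of world) | 8% vs 8% (type I error) | 10% vs 20% | 8% vs 20% | 8% vs 17% |
|---|---|---|---|---|
| 1 / 1 / 1 | 4.94 -> 4.93 | 90.93 -> 90.93 | 98.44 -> 98.44 | 89.27 -> 89.27 |
| 1.5 / 0.8 / 1 | 4.90 -> 4.95 | 90.88 -> 91.02 | 98.42 -> 98.44 | 89.21 -> 89.36 |
| 2 / 0.5 / 1 | 4.78 -> 4.96 | 91.18 -> 91.71 | 98.49 -> 98.60 | 89.45 -> 89.96 |
| 3 / 0.33 / 1 | 4.66 -> 5.06 | 91.36 -> 92.42 | 98.69 -> 98.92 | 89.71 -> 90.80 |

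The last column uses the protocol's rates for histologic-endoscopic mucosal healing. The gain is 0 to 1.1 points at 10% versus 20% and at 8% versus 17%, and 0 to 0.2 points at 8% versus 20%. The simulation standard error at 5% is sqrt(0.05 x 0.95/100,000) = 0.07 points, so 5.06% is compatible with 5%. With region shares of 45/10/45% and odds ratios 2/0.5/1, the gain at 10% versus 20% is 0.3 points (91.04 -> 91.38).

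**4. Sparsity.** Under the assumed shares the smallest of the 12 strata expects 560 x 0.45 x 0.40 x 0.20 = 20 participants, of whom 20.16 x 0.4 = 8 are on placebo. At an overall placebo rate of 8% that is 8.06 x 0.08 = 0.6 remissions, and fewer once the assumed odds ratios are applied. Even so, the first row of the table shows essentially no loss from using 12 strata.

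**The case against.** The strongest reply is that nothing is broken. Protocol 4.2.1 gives balance between groups as the purpose of the stratification variables, and stratified randomisation delivers that whatever the analysis does. A pre-specified CMH test on two of three factors is valid, and any error is against the sponsor. The loss exists only if region is prognostic, which the documents do not show. The Induction Study 2 SAP may justify the omission or already contain a region-stratified analysis. All of this stands, and it limits the point to a minor one. It does not explain why a factor important enough to block on was dropped: the protocol itself fixes the CMH strata and does not list them among the items left to the SAP.

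A reader might infer three stronger things that the documents do not support.

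- That adding region is always a gain at no cost. With no region effect there is no gain, and the strata become sparser.
- That Induction Study 1 needs the same change. Its primary test has the same gap (Protocol 9.4.2.1.2), but at 130 per arm and 30% versus 60% power is already 99.9% and adding region gains nothing. At 50 per arm, in simulation with assumed region effects, adding region lost 0.6 points with no region effect and 0.2 at log-odds of plus or minus 0.4; it gained 1.2 only at plus or minus 0.8.
- That every affected test is confirmatory. The major secondary tests of Induction Study 1 are nominal by design (9.4.2.1.3).

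**Conclusion.** The mismatch in Induction Study 2 is real: region is a randomisation stratum, is absent from the primary and major secondary CMH tests, and its omission is unexplained in the protocol. The consequence is small. Type I error is not inflated: the four-stratum test ran at about 4.7 to 4.9%. No stated sample size or power figure is wrong. The power lost is 0 to about 1 point at 10% versus 20% and at most about 0.2 points at 8% versus 20%. The upper ends require regional odds ratios as extreme as 3 and 0.33. All these sizes rest on assumed region shares and effects. The mismatch is certain on the protocol text; its practical effect is not. This is a low-priority improvement and does not threaten the study's conclusions.

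**What to change.** If Induction Study 2 is still blinded, amend Protocol 9.4.2.2.2 and 9.4.2.2.3, and the Induction Study 2 SAP if it does not already do so. Stratify the CMH test, and any CMH-weighted difference reported with it, by ADT-failure status, region and baseline corticosteroid use. Keep the two-factor version as a sensitivity analysis.

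The documents supplied do not say whether unblinding has taken place. Protocol 6.3 allows selected sponsor personnel to be unblinded at the Week I-12 database lock. If that has happened, leave the planned test as primary, state why region was left out, and report the region-stratified CMH as a sensitivity analysis.

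The cost is a sentence in each place and one more stratification variable, already recorded at randomisation. The only statistical price is sparser strata, which cost essentially no power in the simulation. No change is asked for in Induction Study 1.
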